8.4 Subject Population(s) for Analysis

The purpose of this study is mechanistic in nature, rather than to inform clinical practice *per se*. Accordingly, outcomes assessment is per protocol, with the exception of clinical safety outcomes. If a subject assigned to an active intervention does not maintain $\geq 80\%$ compliance, this presents more than one possibility for analysis. The primary analysis and perhaps most straightforward is to exclude them from the efficacy analysis outright. As an alternative sensitivity analysis, we may include the compliance rate as a covariate or a weight. If we measure specific levels of fat (e.g. RBC omega-3 index, or EPA/DHA levels), we could also consider the change in that outcome from baseline as a functional assay of drug exposure. For safety outcomes, we will conservatively analyze the intention to treat population, defined as all individuals who took at least one dose of at least one study medication during the chronic therapy phase of the study.

9 Safety and Adverse Events

9.1 Definitions

9.1.1 Unanticipated Problems Involving Risk to Subjects or Others

Any incident, experience, or outcome that meets all of the following criteria:

- Unexpected in nature, severity, or frequency (i.e. not described in study-related documents such as the IRB-approved protocol or consent form, prescribing information, the investigators brochure, Standard Operating Procedures and the like).
- Related or possibly related to participation in the research (i.e. possibly related means there is a reasonable possibility that the incident experience, or outcome may have been caused by the procedures involved in the research)
- Suggests that the research places subjects or others at greater risk of harm (including physical, psychological, economic, or social harm).

9.1.2 Adverse Event

An **adverse event** (AE) is any symptom, sign, illness or experience that develops or worsens in severity during the course of the study. Intercurrent illnesses or injuries should be regarded as adverse events. Abnormal results of diagnostic procedures are considered to be adverse events if the abnormality:

- results in study withdrawal
- is associated with a serious adverse event
- is associated with clinical signs or symptoms
- leads to additional treatment or to further diagnostic tests
- is considered by the investigator to be of clinical significance

9.1.3 Serious Adverse Event

Adverse events are classified as serious or non-serious. A **serious adverse event** is any AE that is:

- fatal
- life-threatening
- requires or prolongs hospital stay
- results in persistent or significant disability or incapacity
- a congenital anomaly or birth defect
- an important medical event

Important medical events are those that may not be immediately life threatening, but are clearly of major clinical significance. They may jeopardize the subject, and may require intervention to prevent one of the other serious outcomes noted above. For example, drug overdose or abuse, a seizure that did not result in in-patient hospitalization, or intensive treatment of bronchospasm in an emergency department would typically be considered serious.

All adverse events that do not meet any of the criteria for serious should be regarded as **non-serious adverse events**.

9.2 Intensity

The investigator is responsible for ensuring that AEs are documented on the appropriate page of the CRF according to the following descriptors:

Mild: associated with no limitation of usual activities or only slight discomfort

Moderate: associated with limitation of usual activities or significant discomfort

Severe: associated with inability to carry out usual activities or very marked discomfort

Life-Threatening: represents an immediate threat to life

9.3 Relationship to Study Procedure

The relationship of AEs to study procedures including medications will be assigned by the investigator according to the following guidance. Prior versions of this protocol used less specific guidance to rate the relationship. We feel the rating system below improves upon this because the guidance is more specific, lays out the different questions more clearly, and requires a specific number of criteria to be met.

1. **Unrelated:** The adverse event is clearly attributable to extraneous causes (e.g., underlying disease, environment)
2. **Unlikely Related** (must have 2)
 - (A) Does not have temporal relationship to the study procedure.
 - (B) Could readily have been produced by the subject's clinical state.
 - (C) Could have been attributable to environmental or other interventions.
 - (D) Does not follow known pattern of response to study procedure.
 - (E) Does not reappear or worsen with reintroduction or continued use of the study procedure.
3. **Possibly Related** (must have 2)
 - (A) Has a reasonable temporal relationship to study procedure.
 - (B) Could not readily have been produced by the subject's clinical state.
 - (C) Could not readily have been attributable to environmental or other interventions.
 - (D) Follows a known pattern of response to study procedure.
4. **Probably Related** (must have 3)
 - (A) Has a reasonable temporal relationship to study procedure.
 - (B) Could not readily have been produced by the subject's clinical state or have been due to environmental or other interventions.
 - (C) Follows a known pattern of response to study procedure.
 - (D) Disappears or decreases on cessation of the study procedure or following a remediating intervention (i.e. a reasonable temporal relationship to resolution of the adverse effect).
5. **Definitely Related** (must have all 4)
 - (A) Has a reasonable temporal relationship to study procedure.
 - (B) Could not readily have been produced by the subject's clinical state or have been due to environmental or other interventions.
 - (C) Follows a known pattern of response to study procedure.
 - (D) Disappears or decreases on cessation of the study procedure or following a remediating intervention (i.e. a reasonable temporal relationship to resolution of the adverse effect).

9.4 Adverse Event Reporting Period

The study period during which adverse events must be reported is normally defined as the period from the initiation of any study procedures to the end of the study treatment follow-up. For this study, the study treatment follow-up is defined as 30 days following the last administration of study treatment.

9.5 Preexisting Condition

A preexisting condition is one that is present at the start of the study. A preexisting condition should be recorded as an adverse event if the frequency, intensity, or the character of the condition worsens during the study period.

9.6 General Physical Examination Findings

At screening, any clinically significant abnormality should be recorded as a preexisting condition. At the end of the study, any new clinically significant findings/abnormalities that meet the definition of an adverse event must also be recorded and documented as an adverse event.

9.7 Post-study Adverse Event

All unresolved adverse events should be followed by the investigator until the events are resolved, the subject is lost to follow-up, or the adverse event is otherwise explained. At the last scheduled visit, the investigator should instruct each subject to report any subsequent event(s) that the subject, or the subject's personal physician, believes might reasonably be related to participation in this study. The investigator should notify the study sponsor of any death or adverse event occurring at any time after a subject has discontinued or terminated study participation that may reasonably be related to this study. The sponsor should also be notified if the investigator should become aware of the development of cancer or of a congenital anomaly in a subsequently conceived offspring of a subject that has participated in this study.

9.8 Abnormal Laboratory Values

A clinical laboratory abnormality should be documented as an adverse event if any one of the following conditions is met:

- The laboratory abnormality is not otherwise refuted by a repeat test to confirm the abnormality
- The abnormality suggests a disease and/or organ toxicity
- The abnormality is of a degree that requires active management; e.g. change of dose, discontinuation of the drug, more frequent follow-up assessments, further diagnostic investigation, referral to the patient's primary care physician for further evaluation and management, and the like.

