4.4.2 Objective Safety and Tolerability of Study Therapeutics

We will tabulate objective adverse events (i.e. clinically-significant objective outcomes, such as laboratory abnormalities), as described in the section under Adverse Effects.

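### Section 9.8 makes any laboratory abnormality not overturned on repeat an adverse event; this is wider than 9.1.2 and the 4.4.2 safety endpoint, and no precedence is stated

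*Combined protocol and SAP*

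**What the plan says.** Three places define what counts.

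- **Section 9.8** states: "A clinical laboratory abnormality should be documented as an adverse event if any one of the following conditions is met". The first condition is "The laboratory abnormality is not otherwise refuted by a repeat test to confirm the abnormality". The other two are that the abnormality points to disease or organ toxicity, or is of a degree needing active management. The word abnormality is not defined by grade or threshold, and 9.8 does not require a repeat.
- **Section 9.1.2** first defines an adverse event as something that "develops or worsens in severity during the course of the study". It then says: "Abnormal results of diagnostic procedures are considered to be adverse events if the abnormality" meets one of five conditions. These are study withdrawal, association with a serious adverse event, association with signs or symptoms, that it "leads to additional treatment or to further diagnostic tests", or that it "is considered by the investigator to be of clinical significance". Persistence on repeat is not among them.
- **Section 4.4.2**, under Primary Safety Endpoints, tabulates objective adverse events, described as "clinically-significant objective outcomes, such as laboratory abnormalities". For the detail it points to the adverse-event section, which contains both rules above.

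Section 9.6 also uses clinical significance for examination findings. No section says which rule prevails for laboratory values.

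**The concern.** Because the conditions in 9.8 are alternatives, the first makes the other two largely redundant: any abnormality that has not been overturned already qualifies. The first condition reads like a precondition that was listed as an alternative.

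The contents of a primary safety table then depend on which section the staff follow. Under 9.8 they also depend on whether someone chooses to repeat a test. The study is open-label, so the people choosing know the arm. If an unrepeated value is read as unrefuted, a repeat can only remove an event under the first condition, so unequal repeating could shift the arm counts. Section 9.10 requires every adverse event to be recorded and followed to resolution, stabilization or a finding of no causal link, so minor values also bring work.

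**Working it through.** **1. The same result under the three sections.** Take a mildly out-of-range value with no symptoms and no action taken, judged not clinically significant.

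- Repeated and confirmed: an adverse event under 9.8. Under 9.1.2 it is not one, unless the repeat itself counts as a further diagnostic test, which 9.1.2 leaves open. It falls outside the description in 4.4.2.
- Never repeated: an adverse event under 9.8 if unrepeated is read as unrefuted. It is not one under 9.1.2 or the 4.4.2 description.

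The first case shows that the conflict does not hang on how unrepeated values are read.

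**2. Plan figure.** The documents state no expected rate of laboratory adverse events, so there is nothing to reproduce.

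**3. Inputs.**

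- Panel: complete blood count with differential plus comprehensive chemistry (7.2.2.2). The number of analytes is not given; assumed 14 to 30, with 34 as an upper check.
- Visits: five planned (2K, 2F, 3A, 4K, 4F; Section 7 chart). Experimental treatment starts at 2F (3.1.4), so three of them (3A, 4K, 4F) are on randomized treatment.
- Share of normal values outside the reference range: not given; assumed 5%, half on each side.
- Abnormality is taken to mean any value outside the reference range (assumed).

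**4. Independent results.** With n = analytes × visits:

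- no repeats: P(at least one) = 1 − 0.95^n;
- every abnormal value repeated and required to recur on the same side: per-result probability 0.05 × 0.025 = 0.00125, so P = 1 − 0.99875^n.

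| Analytes | Visits | n | No repeats | All repeated |
|---|---|---|---|---|
| 14 | 3 | 42 | 88.4% | 5.1% |
| 14 | 5 | 70 | 97.2% | 8.4% |
| 22 | 3 | 66 | 96.6% | 7.9% |
| 22 | 5 | 110 | 99.6% | 12.9% |
| 30 | 3 | 90 | 99.0% | 10.6% |
| 30 | 5 | 150 | >99.9% | 17.1% |
| 34 | 5 | 170 | >99.9% | 19.2% |

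**5. Correlated results, new values only.** Section 9.1.2 requires an event to be new or worse. A simulation of 20,000 subjects used three on-treatment visits, between-analyte correlation 0.2 and within-subject correlation 0.5 or 0.8. It counted only values that were not out of range on the same side at one baseline measurement.

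| Analytes | Within-subject correlation | No repeats | All repeated |
|---|---|---|---|
| 14 | 0.5 | 76.2% | 19.7% |
| 14 | 0.8 | 58.3% | 21.4% |
| 22 | 0.5 | 88.2% | 28.7% |
| 22 | 0.8 | 73.4% | 31.6% |
| 30 | 0.5 | 94.3% | 36.2% |
| 30 | 0.8 | 82.3% | 40.0% |

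**6. Weight of one subject.** With 12 and 7 enrolled (8.1.1), one subject is 1/12 = 8.3% of the oil arm or 1/7 = 14.3% of usual care.

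**The case against.** The other side has several fair points.

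- Section 9.1.2 says an abnormal result is an adverse event if a condition is met, not only if. Section 9.8 can be read as a more specific supplement. That softens the word contradiction, but two lists of different width with no precedence still give two counts.
- Section 4.4.2 carries its own clinical-significance filter, so its table is inflated only if 9.8 overrides it. This stands as a condition on the conclusion.
- The first condition can be read as presupposing that a repeat is done. That brings the share down to the right-hand columns above, but a confirmed trivial value still qualifies.
- The safety endpoints are tabulated, and no between-arm safety test is specified. Biased repeat testing is therefore a possibility, not something shown.

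Two stronger readings are tempting and are not supported. A reader might infer that nearly every subject would have a chance laboratory adverse event. That needs the assumed analyte count, the assumed 5% rate, near independence and unrepeated values counted as events. It also ignores the new-or-worse requirement in 9.1.2 and the parallel rule in 9.5. If visits were perfectly correlated, no value would be new after baseline. A reader might also infer that liver or hemoglobin signals would be hidden. The protocol has separate monitoring plans for both (5.4.1.1, 5.4.1.2), and 9.13 evaluates laboratory changes from baseline.

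The hemoglobin and hematocrit samples in the kinetics visits should not be overplayed either. The full chart has nine and the shortened chart eight. Two in each fall on the optional second day, and the baseline visit precedes treatment. Section 7.3.1.1 says they estimate plasma volume, and nothing says they feed the adverse-event table. Equally, 9.8 does not exempt them.

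**Conclusion.** The inconsistency is real and rests on the text alone: the first condition in 9.8 is sufficient by itself, carries no significance test, and is wider than 9.1.2 and the 4.4.2 description, with no order of precedence.

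Its size is conditional. If 9.8 governs and abnormal values are not repeated, about 58% to over 99% of subjects could have at least one such event. The low end counts only new values, with 14 analytes, three visits and strong within-subject correlation; the high end counts all values at five visits under independence. If all are repeated, the share is about 5% to 19% under independence, or 20% to 40% with a new confirmed value under correlation. In the correlated case the confirmed values mostly reflect stable individual set points rather than chance. None of the driving inputs is in the documents, so these ranges show sensitivity to repeat practice and are not predictions. No efficacy analysis is affected.

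**What to change.** Reconcile 9.8, 9.1.2 and 4.4.2 into one definition:

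- Remove non-refutation on repeat as a sufficient condition by itself.
- Keep as sufficient the other two conditions in 9.8 and the five in 9.1.2, so that an abnormality meeting one of them counts even if a later repeat is normal. Making non-refutation a requirement for every laboratory event would be wrong: it would drop a transient abnormality that led to treatment or withdrawal, or accompanied a serious event, and then normalised.
- State that a confirmatory repeat alone is not a further diagnostic test under 9.1.2. The same clarification suits the active-management condition in 9.8, whose examples include further investigation.
- State that hemoglobin and hematocrit samples drawn for plasma-volume estimation count only if they meet this definition.
- Use this definition for the 4.4.2 table.

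The cost is about one paragraph and no added tests. The downside is that minor isolated values appear in laboratory listings rather than in the adverse-event table.

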9.9 Hospitalization, Prolonged Hospitalization or Surgery

Any adverse event that results in hospitalization or prolonged hospitalization should be documented and reported as a serious adverse event unless specifically instructed otherwise in this protocol. Any condition responsible for surgery should be documented as an adverse event if the condition meets the criteria for and adverse event.

Neither the condition, hospitalization, prolonged hospitalization, nor surgery are reported as an adverse event in the following circumstances:

- Hospitalization or prolonged hospitalization for diagnostic or elective surgical procedures for a preexisting condition. Surgery should **not** be reported as an outcome of an adverse event if the purpose of the surgery was elective or diagnostic and the outcome was uneventful.
- Hospitalization or prolonged hospitalization required to allow efficacy measurement for the study.
- Hospitalization or prolonged hospitalization for therapy of the target disease of the study, unless it is a worsening or increase in frequency of hospital admissions as judged by the clinical investigator.

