5.2.2 Exclusions for Conditions Rendering Participation Inadvisable

10. Severe allergy to fish, unless non-allergic response to fish oil is established (n.b. most fish allergies are to the proteins as opposed to the fats, so with highly-purified oils the risk of a true allergy is remote).
11. Known intolerance or contraindication to Vascepa, and if the former is unknown, known intolerance or contraindication to fish oil
12. Any surgical or medical condition that may interfere with absorption, distribution, metabolism, or excretion of EPA or DHA.
13. History of extreme triglyceridemia (TG > 1000 mg/dL) within the past 5 years or a history of pancreatitis from triglyceridemia, regardless of whether it is currently controlled.
14. Medical condition that would prohibit fasting (e.g. diagnosis of insulinoma or postabsorptive hypoglycemia).
15. Significant disinclination to dairy products (e.g. lactose intolerance, inviolable dietary restrictions). All participants will receive a test dose of the fat challenge during the screening visit, which consists of heavy cream and lactase enzyme. Many people with lactose intolerance successfully avert symptoms by correcting their lactase deficiency with lactase supplements. We will allow these people to participate because we will allow them to take their preferred brand and dose of lactase supplement beyond the lactase in the fat challenge if needed. However, we still require that they are able to tolerate the test dose given during screening.
16. History of a non-skin malignancy within the previous 5 years.
17. Uncontrolled thyroid disease.

18. Any major active rheumatologic, pulmonary, or dermatologic disease or inflammatory condition.
19. Major surgery within the previous 6 weeks.
20. Subjects who have undergone any organ transplant.
21. History of illicit drug use within the past 3 years, or regular alcohol use of greater than 14 drinks per week. For clarity, illicit substances are per Federal law or regulations in effect at the time of first approval of this protocol.
22. Women who are breast-feeding.
23. Women of childbearing potential must have a negative urine pregnancy test at screening and baseline visits and be willing to have additional urine pregnancy tests during the study.
24. Sexually active subjects (both women and men) must be willing to use a medically accepted method of contraception from screening visit until month after last dose of study drug

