9.13 Stopping Rules

Based on prior literature and experience with fish oil in general, and EPA-rich oil in particular, we think serious adverse events from the investigational medications are not likely. Safety and tolerability will be evaluated by the incidence, severity, and relationship to study intervention of any adverse events and changes from baseline in laboratory test results, physical examination findings, and vital sign measurements, at any time after the subject has received study intervention. If continuous safety analysis reveals an adverse trend, the Principal Investigator may halt the study independently, or in consultation with the CTRC or IRB, as appropriate. Furthermore, if three or more subjects develop the same serious adverse event related to a study medication or procedure, we will suspend the trial pending a safety review, in consultation with the CTRC and the IRB.

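### The first hospitalization exception in 9.9 has no clause for worsening, so it conflicts with 9.5 over a preexisting condition that worsens and leads to a diagnostic or elective admission

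*Combined protocol and SAP*

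**What the plan says.** Section 9.9 starts from a general rule: an AE that leads to or prolongs hospitalization "should be documented and reported as a serious adverse event unless specifically instructed otherwise in this protocol". It then says: "Any condition responsible for surgery should be documented as an adverse event if the condition meets the criteria for and adverse event".

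A list of exceptions follows, introduced by "Neither the condition, hospitalization, prolonged hospitalization, nor surgery are reported as an adverse event in the following circumstances". The first exception is "Hospitalization or prolonged hospitalization for diagnostic or elective surgical procedures for a preexisting condition". A second sentence in that bullet says surgery is not to be given as the outcome of an AE when it was elective or diagnostic and went without incident. The third exception, for admissions to treat the target disease, is qualified: "unless it is a worsening or increase in frequency of hospital admissions as judged by the clinical investigator". The first has no such qualifier.

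Section 9.5 says: "A preexisting condition should be recorded as an adverse event if the frequency, intensity, or the character of the condition worsens". Section 9.1.2 includes worsening in the definition of an AE, and 9.1.3 classes an AE that needs or lengthens an inpatient stay as serious. Section 9.10 requires all AEs in the study period to be recorded.

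**The concern.** The lead-in to the list removes the condition as well as the admission. The general SAE rule in 9.9 gives way to any specific instruction elsewhere in the protocol, and the first exception is such an instruction. Site staff applying it as written could therefore treat a worsened preexisting condition as neither an AE nor an SAE, provided the admission was for a diagnostic or elective procedure. Because the third exception has a worsening clause and the first does not, a reader could take the difference as deliberate.

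Two processes depend on SAE status. Section 9.11.1 requires any SAE to be notified to the sponsor within 24 hours. Section 9.13 suspends the trial "if three or more subjects develop the same serious adverse event related to a study medication or procedure". An event not classed as an SAE enters neither.

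**Working it through.** The plan gives no figure on this point and no arithmetic settles it, so the check compares the sections case by case. Take a condition present at the start of the study and an admission during the study for a diagnostic or elective procedure.

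1. **Condition unchanged, any procedure.** Under 9.5 and 9.1.2 there is no AE. Under the first exception in 9.9 nothing is reported. The sections agree, and the exception does its proper job.

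2. **Condition worsened, elective surgery.** Under 9.5 and 9.1.2 the condition is an AE, and under 9.1.3 the hospital stay makes it serious. The exception list says neither condition nor admission is reported. The opening paragraph of 9.9 says a condition behind surgery is documented as an AE if it meets the criteria, which this one does. The second sentence of the first bullet points the same way, since it assumes that an AE can lie behind elective surgery. So the AE can be rescued from within 9.9. Neither sentence says whether the admission is then an SAE.

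3. **Condition worsened, non-surgical diagnostic admission.** For illustration: 5.2.1.1 excludes coronary events only within 6 months of baseline, so a subject may enter with older coronary disease, have more frequent symptoms on study, and be admitted for a planned diagnostic work-up. Sections 9.5, 9.1.2 and 9.1.3 make this an AE and an SAE. The first exception says neither the condition nor the admission is reported. The sentence about surgery does not apply, and nothing else in 9.9 offsets the exception. The conflict is direct.

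Case 1 shows that the exception need not be removed. Cases 2 and 3 show what it lacks: the condition on worsening that 9.5 sets and that the third exception already contains.

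**The case against.** The best defence is that the sections can be read together. 9.9 nowhere says that a worsened condition is exempt; that is inferred from silence. A worsened condition meets the AE definition, 9.10 requires it to be recorded, and 9.9 itself keeps the AE criteria for conditions leading to surgery. The word surgical might also govern both diagnostic and elective, in which case a non-surgical diagnostic admission falls outside the exception and stays an SAE. These arguments stand as reasons to call this an ambiguity. They do not remove it. The documents do not say which sentence governs, the narrower grammar is only one possible reading, and even that reading leaves the SAE status of the admission open in case 2.

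Stronger readings are tempting but are not supported.

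- **That 9.9 hides serious events from the safety endpoint.** Sections 9.5 and 9.10 require recording, and 4.4 tabulates AEs, so a worsened condition can still reach the tables. Other routes remain: 9.1.2 and 9.8 capture laboratory abnormalities that lead to further investigation, and the IRB route in 9.11.2 covers unexpected, related AEs whether serious or not.
- **That the 9.13 suspension rule is disabled.** Missing the trigger needs the same related SAE in three subjects, with at least one lost through this exception. 9.13 also lets the principal investigator halt on an adverse trend without any count. A probability of missing the trigger would need event rates and a loss fraction that the documents do not give.
- **That the third exception lets a new admission for triglyceridemia go unreported.** The eligibility criteria exclude recent extreme triglyceridemia "or a history of pancreatitis from triglyceridemia, regardless of whether it is currently controlled", so few subjects will have a background of such admissions. That points towards reporting: a first admission is itself an increase in frequency under the clause in that exception.

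**Conclusion.** The conflict is real but minor. Read with its lead-in, the first exception in 9.9 takes both the admission and the condition out of AE reporting and makes no allowance for worsening, contrary to 9.5, 9.1.2 and 9.1.3. The surgery sentence in 9.9 resolves this only in part. On a literal reading, a worsened preexisting condition with a non-surgical diagnostic admission could go unreported to the sponsor as an SAE and uncounted in 9.13.

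The conclusion rests on the text alone, and assumes that diagnostic admissions in the first exception include non-surgical ones. The size cannot be computed from the documents. It is likely to be small: the minimum enrolment is 19, and the exclusion of subjects anticipating major surgery (criterion 29) narrows the situations that could arise. Leaving out a planned admission for an unchanged condition is consistent with 9.5 and is not criticised here.

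**What to change.** Add to the first exception in 9.9: *unless the condition has worsened in frequency, intensity or character during the study period (see 9.5), in which case the condition is reported as an adverse event and the hospitalization as a serious adverse event.*

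The third exception needs no change. The exemption should not be limited to procedures planned before enrolment. If every other admission were then reported, a stable condition with an elective procedure scheduled later would become an AE and an SAE, which 9.5 does not intend.

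The cost is one clause in an amendment and possibly one or two extra SAE reports. Treatment, eligibility and analysis are unaffected.
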